12.6 UNBLINDING OF TEST ARTICLE

Not Applicable.

12.7 FOLLOW-UP OF SUBJECTS WITH ADVERSE EVENTS

For subjects who are experiencing ongoing unresolved AE at the time of their study completion or early discontinuation from the study, it is recommended that the Investigator schedule an appropriate follow-up visit in order to determine the outcome of the event. Any additional data must be documented and available to the sponsor who will determine when the data need to be documented on the case report forms.

13. INVESTIGATOR OBLIGATIONS

The Principal Investigator will comply with the commitments outlined in the Statement of Investigator (Form FDA 1572) and with Good Clinical Practices (GCP) and with all applicable regulatory requirements as outlined in Appendix 18.6 of this protocol.

14. SPONSOR AND MONITOR RESPONSIBILITIES

The Sponsor will designate a monitor to conduct the appropriate site visits at the appropriate intervals. The clinical investigation will be monitored to ensure that: the rights and well being of the subjects are protected; the reported data are accurate, complete, and verifiable from the source documents; and the study is conducted in compliance with the current approved protocol [and amendment(s), if applicable], with current GCP, and with applicable regulatory requirements.

All studies will have a site initiation. Monitoring will be conducted periodically while the clinical study is ongoing. Monitoring methods may include site visits, telephone, written and fax correspondence. The Study Manager and/or assigned study monitor will contact each site at appropriate intervals. The Study Manager will determine the frequency of site visits. Close-out visits will take place after the last visit of the last subject.

17. STUDY PLAN

Table 17-1: Study Procedures by Treatment Plan

Parameter	Screening Run-in Period		Treatment Period Weekly Visits (±1 day)		End of Treatment Weekly Visits	
	Trial Visit Screen/Run- in Visit 1	Screen/Run- in Visit 2	Study Visit 1	Study Visits 2 to 12	Study Visit 13 ^c	Study Visit 14
Informed Consent	X					
Quality of Life Questionnaires (CWIS, EQ-5D)			X	X ^d	X ^d	X ^e
Register with sealed envelope (IWR)	X	X				
Demography	X					
Inclusion/Exclusion Criteria	X	X				
Medical Hx Including Ulcer Disease Hx	X					
Physical Exam including Vital Signs	X					
Selection of Target Ulcer	X					
VAS Pain Assessments	X	X	X	X	X	X ^e
Examine Target Ulcer for infection	X	X		X		
Photography and Measure Ulcer Size	X	X		X	X	X
Great Toe Pressure or ABI (or TcPO ₂)	X					
Blood collection for hematology, chemistry, pre-albumin and HbA _{1c}	X					
Urine Pregnancy Test	X ^a					X ^a
Randomization			X ^b			
Application of NPWT & Device questions			X	X		
Target ulcer & peri-wound assessment			X	X	X	X
Ulcer Care	X	X	X	X	X	
Subject Satisfaction Questionnaire						X
Assessment of Adverse Events or DevD	X		Assessed throughout the trial			
Concomitant Medications	X		Assessed throughout the trial			

a If subject is female of child-bearing potential, a pregnancy test is required.

b Subjects will be randomized only after the Investigator has verified that all inclusion/exclusion criteria are met.

c Subject's target ulcer judged to have not closed at Visit 13 will not complete the procedures for this Visit, but will complete the End of Treatment Assessment or Early Discontinuation Visit 14 procedures.

d Subjects to complete CWIS and EQ-5D only if the target ulcer is closed or will be surgically closed during the treatment period.

e Subjects to complete CWIS, EQ-5D and VAS assessments only if the target ulcer remained open during the treatment period.

CONFIDENTIAL DOCUMENT
This document contains confidential information, which is the property of Smith & Nephew, Inc. Do not copy, disclose, or circulate without written authorization from the appropriate Smith & Nephew personnel

18. APPENDICES

18.1 CONTRAINDICATIONS TO NEGATIVE PRESSURE WOUND THERAPY (NPWT)

The use of PICO is contraindicated in the presence of:

- Subjects with malignancy in the wound bed or margins of the wound (except in palliative care to enhance quality of life).
- Previously confirmed and untreated osteomyelitis.
- Necrotic tissue with eschar present.
- Exposed arteries, veins, nerves or organs.
- Anastomotic sites.
- Emergency airway aspiration.
- Pleural, mediastinal or chest tube drainage.
- Surgical suction.

The use of tNPWT is contraindicated in the following:

- Placing foam dressings directly in contact with exposed blood vessels, anastomotic sites, organs, or nerves.
- Malignancy in the wound
- Untreated osteomyelitis
- Non-enteric and unexplored fistulas
- Necrotic tissue with eschar present
 - NOTE: After debridement of necrotic tissue and complete removal of eschar, tNPWT may be used.

CONFIDENTIAL DOCUMENT
This document contains confidential information, which is the property of Smith & Nephew, Inc. Do not copy, disclose, or circulate without written authorization from the appropriate Smith & Nephew personnel.

18.2 ARANZ SILHOUETTE

Silhouette is a portable device that easily allows capture of information about a subject's ulcer, which is analyzed, managed, and stored in a central database. Information captured includes photographic images, quantitative measures, and other ulcer assessment data input by the clinician, all obtained with no subject contact. Silhouette builds that information into an electronic record for printing, electronic uploading to the Sponsor's database, and archiving. Information about the ulcer's measurement history is available on this system so that the serial progression of wound status can be calculated and presented. Most of this process is automated.

18.3 ROUTINE LABORATORY TESTS

The following laboratory tests will be performed at the Screening visit to confirm eligibility:

Hematology: Red Blood Cell (RBC) count, Hemoglobin, Hematocrit, Platelets, White Blood Cell (WBC) total count, and differential (%) including absolute counts ($\times 10^9/L$)

Blood Biochemistries: Sodium, Potassium, Calcium, Creatinine, Total Bilirubin, ALT, AST, Alkaline Phosphatase, Albumin, Total Protein, Urea, Glucose, and HbA_{1c}

Additional Chemistries: Pre-albumin

Urine Pregnancy Test to be performed at Screening Run-in Visit 1 & Exit Visit (*only for females that are not premenarchal, not postmenopausal, or surgically sterile*)

18.4 VISUAL ANALOGUE SCALE (VAS) FOR PAIN

The Visual Analogue Scale is simply a line of fixed length, on which the subject marks their subject experience of pain with a single stroke using a pen.

At each specified visit the degree of pain associated with removal of the dressing, application of the NPWT and dressing wear to the target leg will be assessed using a visual analog scale (VAS). The subject will record their level of pain on a 100 mm visual analog scale, similar to the one illustrated above. The scale will be marked ‘no pain’ on the left side of the scale and ‘severe pain’ at the right end of the scale. The subject will be instructed to place a vertical mark on the scale, using a black ball-point pen, indicating their level of pain at the visit.

The Investigator, or designee, will measure the distance (in millimeters) from the left end of the VAS line to the vertical line drawn by the subject. This value will be entered in the subject’s CRF as a measure of the pain associated with the target ulcer.

18.5 EQ-5D

The EQ-5D-5L still consists of 2 pages – the EQ-5D-5L descriptive system and the EQ visual Analogue scale (EQ VAS). The descriptive system comprises the same 5 dimensions as the EQ-5D-5D-3L (mobility, self-care, usual activities, pain/discomfort, anxiety/depression). However, each dimension now has 5 levels: no problems, slight problems, moderate problems, severe problems, and extreme problems.

[figure not shown]
The respondent is asked to indicate his/her health state by ticking (or placing a cross) in the box against the most appropriate statement in each of the 5 dimensions. This decision results in a 1-digit number expressing the level selected for that dimension. The digits for 5 dimensions can be combined in a 5-digit number describing the respondent’s health state.

Under each heading, please tick the ONE box that best describes your health TODAY.

- MOBILITY**
- I have no problems in walking about
 - I have slight problems in walking about
 - I have moderate problems in walking about
 - I have severe problems in walking about
 - I am unable to walk about
- SELF-CARE**
- I have no problems washing or dressing myself
 - I have slight problems washing or dressing myself
 - I have moderate problems washing or dressing myself
 - I have severe problems washing or dressing myself
 - I am unable to wash or dress myself
- USUAL ACTIVITIES** (e.g. work, study, housework, family or leisure activities)
- I have no problems doing my usual activities
 - I have slight problems doing my usual activities
 - I have moderate problems doing my usual activities
 - I have severe problems doing my usual activities
 - I am unable to do my usual activities
- PAIN / DISCOMFORT**
- I have no pain or discomfort
 - I have slight pain or discomfort
 - I have moderate pain or discomfort
 - I have severe pain or discomfort
 - I have extreme pain or discomfort
- ANXIETY / DEPRESSION**
- I am not anxious or depressed
 - I am slightly anxious or depressed
 - I am moderately anxious or depressed
 - I am severely anxious or depressed
 - I am extremely anxious or depressed

- We would like to know how good or bad your health is TODAY.
- This scale is numbered from 0 to 100.
- 100 means the best health you can imagine.
0 means the worst health you can imagine.
- Mark an X on the scale to indicate how your health is TODAY.
- Now, please write the number you marked on the scale in the box below.

YOUR HEALTH TODAY =

CONFIDENTIAL DOCUMENT

18.6 CWIS²⁵

The C.W.I.S. is a condition-specific quality of life tool that has been developed at the Wound Healing Research Unit in Cardiff. The tool has undergone extensive piloting to establish the psychometric properties of the tool. The tool gives a profile of scores for Well-Being, Physical Symptoms and Daily Living and Social Life. Physical Symptoms and Daily Living, and Social Life are assessed for both the experience of a given symptom and the associated stress experienced by the individual. In addition, an indication of overall HRQoL is assessed using a global scale, together with an indication of the satisfaction with that HRQoL.

CONFIDENTIAL DOCUMENT
This document contains confidential information, which is the property of Smith & Nephew, Inc. Do not copy, disclose, or circulate without written authorization from the appropriate Smith & Nephew personnel.

Overall Quality of Life
How would you rate your overall quality of life during the past week?
Please circle a number below
How good is your quality of life?
My quality of life is the worst possible 0 1 2 3 4 5 6 7 8 9 10 My quality of life is the best possible
How satisfied are you with your overall quality of life?
Not at all satisfied 0 1 2 3 4 5 6 7 8 9 10 Very satisfied
Overall Comment(s)

Wound Healing Research Unit
University of Wales College of Medicine

Cardiff Wound Impact Schedule

© Copyright © Smith & Nephew, Inc. All rights reserved. 2016

Form 001

Total

© Copyright © Smith & Nephew, Inc. All rights reserved. 2016

CONFIDENTIAL DOCUMENT
 This document contains confidential information, which is the property of Smith & Nephew, Inc. Do not copy, disclose, or circulate without written authorization from the appropriate Smith & Nephew personnel

The following questionnaire is concerned with the effects that your wound(s) has/have on your daily life. Please answer the questions carefully by placing a tick in the box which most closely reflects how you feel. It should take about ten minutes to complete.

If you are unsure about how to answer a question, please tick the answer which is closest to how you feel. All answers are confidential.

Personal Details

Parent initials: _____ Sex: M F

Parent Number: _____

Date of Birth: D D M M Y Y

Assessment 1st 2nd 3rd 4th 5th

Assessment Date: D D M M Y Y Next Assessment Due: D D M M Y Y

Wound status: Healed Not healed

Do you live on your own? Yes No

How often do you see your family and friends?

Once a day Once a month

Once a week Less than once a month

Total: _____

Social Life

How stressful has this experience been for you?

	Not at all Not applicable	Slightly	Moderately	Quite a bit	Very
Difficulty getting out and about					
Helping more on others					
Your family/friends being over-protective					
Unable to enjoy your usual social life (eg hobbies)					
Limited contact with family/friends					
Not going out for fear of bumping your wound site					
Wanting to withdraw from people					
Total					

Social Life

Have you experienced any of the following during the past week?

	Not at all Not applicable	Seldom	Sometimes	Frequently	Always
Difficulty getting out and about					
Helping more on others					
Your family/friends being over-protective					
Unable to enjoy your usual social life (eg hobbies)					
Limited contact with family/friends					
Not going out for fear of bumping your wound site					
Wanting to withdraw from people					
Total					

Well-being

To what extent do you agree/disagree with the following statements?

	Strongly Disagree	Disagree	Not sure	Agree	Strongly Agree
I feel anxious about my wound(s)					
I feel frustrated at the time it is taking for the wound(s) to heal					
I am confident that the wound(s) I have will heal					
I worry that I may get another wound in the future					
The appearance of the wound site is upsetting					
I feel anxious about bumping the wound site					
I worry about the impact of the wound(s) on my family/friends					
Total					

Physical Symptoms and Daily Living

Have you experienced any of the following during the past week?

	Not at all Not applicable	Seldom	Sometimes	Frequently	Always
Disturbed sleep					
Difficulty in bathing					
Immobility around the home					
Immobility outside the home					
Leakage from the wound(s)					
Pain from the wound site					
Discomfort from the bandage/dressing					
Unpleasant odour or smell from the wound(s)					
Problems with everyday tasks (eg shopping)					
Difficulty in finding appropriate footwear					
Problems with the amount of time needed to care for the wound site					
Financial difficulties as a result of the wound(s)					
Total					

Physical Symptoms and Daily Living

How stressful has this experience been for you?

	Not at all Not applicable	Slightly	Moderately	Quite a bit	Very
Disturbed sleep					
Difficulty in bathing					
Immobility around the home					
Immobility outside the home					
Leakage from the wound(s)					
Pain from the wound site					
Discomfort from the bandage/dressing					
Unpleasant odour or smell from the wound(s)					
Problems with everyday tasks (eg shopping)					
Difficulty in finding appropriate footwear					
Problems with the amount of time needed to care for the wound site					
Financial difficulties as a result of the wound(s)					
Total					

18.7 IMPACT OF THE DEVICE ON ASPECTS OF DAILY LIVING AND SATISFACTION WITH DEVICE THERAPY

Subject response to a custom questionnaire to assess the impact of treatment with the device on subject's daily activities and satisfaction with the device.

Activities of Daily Living

1. It was a burden to come to the wound care clinic for my dressing change.
 - a. Strongly Disagree/Disagree/Neutral/Agree/Strongly Agree
2. The use of the NPWT device restricted many of my normal activities (i.e., sleeping, walking, eating, cleaning, moving around, etc.).
 - a. Strongly Disagree/Disagree/Neutral/Agree/Strongly Agree
3. The NPWT device was cumbersome and interfered with my mobility.
 - a. Strongly Disagree/Disagree/Neutral/Agree/Strongly Agree
4. I was able to work and do my normal daily activities while being treated with the NPWT device.
 - a. Strongly Disagree/Disagree/Neutral/Agree/Strongly Agree
5. The NPWT device was easy to use.
 - a. Strongly Disagree/Disagree/Neutral/Agree/Strongly Agree
6. The NPWT device was light-weight and portable.
 - a. Strongly Disagree/Disagree/Neutral/Agree/Strongly Agree
7. I wish the NPWT device was more light-weight and portable.
 - a. Strongly Disagree/Disagree/Neutral/Agree/Strongly Agree
8. After treatment with the NPWT, how did your overall activity level change?
 - a. Less Active/Stayed the Same/More Active

Noise from the device

1. The noise from the NPWT device was bothersome.
 - a. Strongly Disagree/Disagree/Neutral/Agree/Strongly Agree
2. How often did the noise from the NPWT device bother you?
 - a. Never/Rarely/Several times per day/Most of the time/All of the time

Sleep Disruption

1. The use of the NPWT device was disruptive to my sleep.
 - a. Strongly Disagree/Disagree/Neutral/Agree/Strongly Agree
2. Did the noise from the NPWT device bother you when you were trying to go to sleep?
 - a. Never/1–2 nights per week/2–4 nights per week/4–6 nights per week/Every night
3. How often did the use of the NPWT device disrupt your sleep?
 - a. Never/1–2 nights per week/2–4 nights per week/4–6 nights per week/Every night
4. I often had to turn off the device to try and go to sleep?
 - a. Never/1–2 nights per week/2–4 nights per week/4–6 nights per week/Every night

Discomfort

1. The NPWT was comfortable to wear?
 - a. Strongly Disagree/Disagree/Neutral/Agree/Strongly Agree
2. What was your overall discomfort while using the NPWT device?
 - a. No discomfort/minimal discomfort/low level of discomfort/moderate level of discomfort/high level of discomfort

Perceived Effectiveness/Satisfaction

1. The use of the NPWT device helped my ulcer heal faster?

- a. Strongly Disagree/Disagree/Neutral/Agree/Strongly Agree
2. I would use the NPWT device again on another wound in the future?
 - a. Strongly Disagree/Disagree/Neutral/Agree/Strongly Agree
3. I am overall satisfied with the NPWT device used to treat my ulcer?
 - a. Strongly Disagree/Disagree/Neutral/Agree/Strongly Agree

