All responses to the exit survey will be summarized by treatment and by individual tNPWT device. In addition, where appropriate, a Cochran-Mantel-Haenszel test will be used to test for a difference in subject response between treatments for individual survey questions.

Remaining exploratory endpoints, including the estimation of tissue types present, condition of peri-wound skin and the pain on removal of dressing and at initiation of, and during, therapy, will be summarized by assessment and treatment.

CONFIDENTIAL DOCUMENT
This document contains confidential information, which is the property of Smith & Nephew, Inc. Do not copy, disclose, or circulate without written authorization from the appropriate Smith & Nephew personnel

Other Planned Analysis

At minimum, all data collected will be summarized and listed by treatment; where appropriate data collected will also be summarized by tNPWT device. Additional subsets for summaries may be utilized as a result of the analyses relating to the primary and secondary objectives.

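### Three of the four sleep items in the custom exit questionnaire have overlapping answer boxes, so 2 and 4 nights per week each fit two boxes and the middle categories of the by-treatment summaries are ambiguous.

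*Protocol*

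**What the plan says.** Protocol 18.7 describes the instrument as "Subject response to a custom questionnaire to assess the impact of treatment with the device on subject's daily activities and satisfaction with the device". It is given once, at Visit 14 (Protocol 9.1.6 and Table 17-1; SAP 2.2 calls it the Exit Survey).

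The sleep block has four items:

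- Item 1, "The use of the NPWT device was disruptive to my sleep", uses a five-point agreement scale.
- Item 2 asks about device noise when falling asleep.
- Item 3 asks "How often did the use of the NPWT device disrupt your sleep".
- Item 4 reads "I often had to turn off the device to try and go to sleep".

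Items 2, 3 and 4 all carry the same options: "Never/1–2 nights per week/2–4 nights per week/4–6 nights per week/Every night".

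On analysis, Protocol 10.3.3 states "All responses to the exit survey will be summarized by treatment and by individual tNPWT device" and adds that, where appropriate, "a Cochran-Mantel-Haenszel test will be used to test for a difference in subject response between treatments for individual survey questions". SAP 4.11 likewise summarizes every exit-survey item by treatment, and also by center, wound type and baseline mobility. It then lists five items for a Cochran-Mantel-Haenszel test. The only sleep item among them is item 1.

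**The concern.** Answer boxes for an ordinal count should be exhaustive and mutually exclusive. Here the upper end of one box is the lower end of the next, at 2 and again at 4. Two subjects with the same experience can therefore give different answers, both correct. Once the box is ticked, the count behind it cannot be recovered, and because the form is completed only once, no later answer can settle it.

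What is at stake is the readability of a few exploratory tables. Impact of the device on daily living is a listed exploratory objective, and these three items are the only ones in the questionnaire that express sleep disturbance in nights per week. A reader comparing the middle categories between arms could not tell a difference in nights from a difference in how ties were resolved.

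**Working it through.** The plan states no figure on this point, so there is nothing to reproduce. The check maps each possible whole number of nights to the printed boxes and counts how many it fits.

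**Input.** The five options in Protocol 18.7, sleep items 2 to 4.

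| Nights per week | Boxes that fit |
|---|---|
| 0 | Never |
| 1 | 1–2 |
| 2 | 1–2 or 2–4 |
| 3 | 2–4 |
| 4 | 2–4 or 4–6 |
| 5 | 4–6 |
| 6 | 4–6 |
| 7 | Every night |

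Two of the eight values fit two boxes. The other six fit exactly one. Never and Every night are unaffected.

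**Is there a tie rule?** SAP 4.3 sets out coding for CWIS (derived variables 22 and 23), EQ-5D (24 and 25) and the wound assessment tool (36). It has no entry for the exit survey. Protocol 18.7 gives no instruction to the subject either.

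**Size in general.** Let p(k) be the share of subjects with k nights. The share with two valid boxes is p(2) + p(4). If every subject at a tie switches from the lower to the higher box, the 1–2 box loses p(2), the 4–6 box gains p(4), and the 2–4 box changes by p(2) − p(4). The documents give no distribution of nights, so the size is unknown. It is zero if nobody has 2 or 4 nights and grows with p(2) and p(4).

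**Illustration, assuming an even spread,** p(k) = 1/8 = 12.5% for k = 0 to 7. Share with two valid boxes: 2/8 = 25%.

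| Box | Ties always go lower | Ties always go higher |
|---|---|---|
| Never | p(0) = 12.5% | 12.5% |
| 1–2 | p(1)+p(2) = 25.0% | p(1) = 12.5% |
| 2–4 | p(3)+p(4) = 25.0% | p(2)+p(3) = 25.0% |
| 4–6 | p(5)+p(6) = 25.0% | p(4)+p(5)+p(6) = 37.5% |
| Every night | p(7) = 12.5% | 12.5% |

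With identical experience, 12.5 points move between 1–2 and 4–6, and 2–4 does not change.

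**Collapsed categories.** Never / 1–6 / Every night gives 12.5% / 75.0% / 12.5% under either rule (25.0 + 25.0 + 25.0 = 75.0 and 12.5 + 25.0 + 37.5 = 75.0). The overlap has no effect at that level.

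**The case against.** The strongest reply is that this hardly matters. The items are exploratory, any misplacement is to a neighbouring box, and both arms see the same form. The questionnaire is filled in at the end of up to 12 weeks of therapy, so a subject is recalling a typical week. The answer may be an average such as 2.5 nights, which fits only one printed box. Sleep and therapy interruption are also captured elsewhere: CWIS asks about disturbed sleep, both how often and how stressful (Protocol 18.6), and interruption of study therapy is recorded in hours and summarized by treatment (SAP 4.3, derived variables 40 and 42; SAP 4.12). All of this stands, and it keeps the point small. It does not remove the overlap, because many subjects will still think in whole nights.

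A reader might infer more than the documents support, in three ways.

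- **That a planned test is compromised.** Protocol 10.3.3 permits tests on individual questions only where appropriate, and the items SAP 4.11 names include only sleep item 1.
- **That the comparison between arms is biased.** This would need the arms to resolve ties differently. The trial is open-label, so attitude to a known device could in principle influence the choice, but nothing in the documents shows that it would.
- **That the 2–4 box could hold anything from 12.5% to 37.5% for the same experience.** Under the even spread this needs opposite choices at the two edges: 2 going down and 4 going up for the low figure (p(3) = 1/8), the reverse for the high one (p(2)+p(3)+p(4) = 3/8). Nothing in the documents suggests that pattern.

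**Conclusion.** The overlap is real, and it sits in items 2, 3 and 4. It makes the 1–2, 2–4 and 4–6 categories of the exit-survey summaries ambiguous. The expected consequence is extra noise between adjacent boxes in exploratory tables. No primary or secondary endpoint, sample size or significance level is affected, and neither is any test the SAP names.

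The 25% and 12.5-point figures rest on an assumed even spread over whole nights and on everyone resolving ties the same way. They show the mechanism and do not forecast this trial. Nor is the information wholly lost: the three-level version is sound, although the five-level detail cannot be restored for completed forms. The importance is low, and the point is worth raising because the correction is simple.

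**What to change.** In items 2, 3 and 4 of Protocol 18.7, print Never / 1–2 / 3–4 / 5–6 / Every night, and instruct the subject to give the nearest whole number of nights in a typical week. The instruction is needed because the new boxes would otherwise leave gaps for averages such as 2.5 or 4.5.

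For forms already completed, show the five boxes as printed, with a footnote stating that 2 and 4 nights each fit two boxes. If old and new forms are pooled, add a Never / 1–6 nights / Every night summary. No added hypothesis test is needed.

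The cost is an edit to the form and the eCRF. Because the items are printed in a protocol appendix, the change would go through as an amendment with IRB/IEC approval (Protocol 18.12, item 7) and could travel with another one. The instrument is custom, and neither document describes a published scoring that the edit would break. The downsides are two form versions if recruitment has begun, and coarser categories in the pooled table, which puts 1 night and 6 nights in one group.
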